### **3. RESEARCH DESIGN AND METHODS**

#### **3.1 Overview of Design**

All participants will be patients that have been screened at the Department of Dermatology at the George Washington Medical Faculty Associates. Individuals taking part in the study will meet all of the inclusion criteria and none of the exclusion criteria (see Section 3.2). After completing the screening phase, subjects will receive 2 punch biopsy wounds on the thighs of each leg in their first study visit. Prior to dressing the wounds, 1 wound will be treated with primary closure, while the other will be treated with Nuvagen™ (collagen powder). Each wound will continue to be treated with the treatment designated in visit 1 (primary closure or collagen powder) for the duration of the 12-week study. After visit 1, patients will be provided with instructions and supply for daily self-administration of Nuvagen™ (collagen powder) for the wound designated for collagen powder treatment. Subjects will return weekly for 2 weeks, for suture removal if needed, photographs, wound measuring, assessment of healing, assessment of adverse events, and determination for need of further treatment with Nuvagen™ (collagen powder). Subjects will then return at week 4 for 2 additional punch biopsies at the same sites wounded at the first visit, and will be provided with similar treatment instructions as they were provided in week 1. Patients will return in 2 weeks (visit 5) for suture removal, photographs, wound measuring, assessment of healing, assessment of adverse events, and determination for need of further treatment with Nuvagen™ (collagen powder). The last study visit will be a 6 weeks after visit 5,

during which wounds will be measured and assessed for healing, while subjects will be photographed and assessed for adverse events.

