**Patient Overall Assessment Scale.** Patients will assess the overall improvement of their wounds using a 4-point scale, where 1 = excellent improvement, 2 = good / moderate improvement, 3 = no change, 4 = worsening. This assessment will be performed prior to every follow up visit after wounding at week 0, and upon study completion for each wound. Improvement will be indicated by a decrease by  $\geq 1$  point compared to the previous assessment. Worsening will be indicated by an increase in this scale by  $\geq 1$  point compared to the previous assessment. Patients will also be asked preference between the NuvagenTM (collagen powder) and primary closure.

**Pruritus Numerical Rating (NRS) Scale.** Patients will also score pruritus on the validated NRS scale, which ranges from 1-10. This assessment will be performed prior to every follow up visit after wounding at week 0, and upon study completion for each wound. Improvement will be indicated by a decrease by  $\geq 2$  points compared to the previous assessment. Worsening will be indicated by an increase in this scale by  $\geq 2$  points compared to the previous assessment.

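### Patient ratings are labelled improved or worsened against the previous rating, with no restart after both sites are re-biopsied at visit 4, so 16 of 64 comparisons per scale set a new wound against an old one

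*Combined protocol and SAP*

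**What the plan says.** Section 4.2, Wound specific variables, defines two patient-reported scales.

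- **Patient Overall Assessment Scale.** The patient rates each wound in one of four categories, all of them worded as change: "where 1 = excellent improvement, 2 = good / moderate improvement, 3 = no change, 4 = worsening". A fall of at least 1 point counts as improvement and a rise of at least 1 point as worsening, each judged against the rating before it ("point compared to the previous assessment. Worsening will be indicated by an increase in this scale by" …).
- **Pruritus NRS.** "Patients will also score pruritus on the validated NRS scale, which ranges from 1-10". The rule has the same form with a 2-point threshold ("points compared to the previous assessment. Worsening will be indicated by an increase in this scale by" …).

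On timing, the section says of each scale: "This assessment will be performed prior to every follow up visit after wounding at week 0". A rating at study completion is also required. Table 1 marks both scales at visits 2 to 6, which are weeks 1, 2, 4, 6 and 12.

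Section 3.1 adds a second wounding: "Subjects will then return at week 4 for 2 additional punch biopsies at the same sites wounded at the first visit". Section 3.4 repeats this for visit 4, and each site then gets the same treatment as at visit 1. No section restarts the reference rating after the second wounding or separates the two healing periods for these scales.

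Section 4.3 limits the analysis to description and names patient experience and preference among the things to be looked at. Which of the two treatments the patient prefers is a separate question ("Patients will also be asked preference between the" …).

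**The concern.** A label based on the previous rating makes sense while both ratings describe the same wound. After visit 4 they do not: the old wound has been cut out and a new one made at the same site. A label that spans that visit mixes the healing of the first wound with the early course of the second, and part of any shift may come from the study's own procedure. Section 5.2 itself lists itching as a risk of the biopsy, so the pruritus label is exposed as well as the overall one.

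The between-treatment reading is also at stake. The label depends on where each wound stood before the second biopsy. If one treatment had the better last rating on the first wound, and the two new wounds are then rated the same, the treatment that had done better gets the less favourable label.

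A second, conditional question concerns the overall scale only. Its categories already describe change, and the protocol does not tell the patient since when. The phrase about the previous assessment governs the label computed from two ratings, not the question the patient answers. If patients judge change since their last visit, the label becomes a change in reported change and can disagree with what the patient has just said.

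**Working it through.** The plan gives no figure of its own here, so the check is a count.

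**Inputs.** 8 patients (section 3.2); 2 wounds per patient, one collagen and one sutured (section 3.4); visit intervals of 1, 1, 2, 2 and 6 weeks (section 3.4); both scales at visits 2 to 6 (Table 1); re-biopsy at week 4 (section 3.1).

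**Step 1: schedule.** Adding the intervals gives weeks 0, 1, 2, 4, 6 and 12, which agrees with Table 1. Each wound has 5 ratings and so 5 − 1 = 4 consecutive comparisons.

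**Step 2: comparisons per scale.** 8 × 2 × 4 = 64.

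**Step 3: comparisons that cross the re-biopsy.** One per wound: 8 × 2 × 1 = 16, and 16/64 = 25%. Over both scales this is 32 of 128.

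- If the week 4 rating comes before the biopsy, the crossing pair is week 4 to week 6.
- If it came after the biopsy, the crossing pair would be week 2 to week 4. The count is still 16.
- If the study-completion rating were a sixth one separate from visit 6, the total would be 8 × 2 × 5 = 80 and the share 16/80 = 20%. Table 1 shows five ratings and visit 6 is the last visit, so 64 is the natural count.

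**Step 4: what remains.** 64 − 16 = 48 comparisons lie within one wounding cycle. With the week 4 rating before the biopsy, these are 8 × 2 × 2 = 32 in the first cycle (weeks 1 to 2 and 2 to 4) and 8 × 2 × 1 = 16 in the second (weeks 6 to 12).

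**Step 5: opposite labels for equal ratings.** Apply the overall-scale rule across the biopsy:

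| Wound | Last rating, old wound | First rating, new wound | Shift | Label |
|---|---|---|---|---|
| A | 1 | 2 | +1 | worsened |
| B | 3 | 2 | −1 | improved |

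The patient rates the two new wounds the same, yet the labels are opposite. This does not depend on the reference period the patient has in mind. The same happens on the pruritus scale whenever one earlier score is at least 2 points below, and the other at least 2 points above, a common later score.

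**Step 6: the conditional point.** Assume the patient answers since the last visit. There are 4 × 4 = 16 possible (previous, current) pairs on the overall scale. Four have equal ratings and get neither label. Of the other 12, the label agrees with the current answer in 8 and disagrees in 4:

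| Previous, current | Label | Patient's current answer |
|---|---|---|
| 1, 2 | worsened | moderate to good improvement |
| 1, 3 | worsened | no change |
| 2, 3 | worsened | no change |
| 4, 3 | improved | no change |

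Only the first is a strict reversal. These are counts of possible patterns, not expected frequencies.

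**The case against.** The strongest reply is that nothing reported need depend on the labels. The analysis is descriptive, section 4.3 does not say that the labels will be tabulated, pooled or compared by treatment, and nothing stops the raw categories from being reported. This stands in part: the ratings are kept in the study database, so labels can be recomputed, and this limits the harm. It does not dispose of the point, because the labels are the plan's only definition of improvement and worsening for the patient experience that section 4.3 says will be examined.

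A second reply is that both wounds are re-biopsied at the same visit, so the comparison between them stays fair. That holds for the raw ratings of the two new wounds. It does not hold for the labels, as Step 5 shows.

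A third reply is that the reference period may be printed on the patient form, which is not among the documents, and that a rating of overall improvement can be read as cumulative since wounding. This is fair. On that reading most labels within one cycle can be taken as visit-to-visit change, which is why the second point is only conditional.

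A reader might also infer that sections 3.4 and 4.2 contradict each other on the week 4 rating, since section 3.4 lists it after the biopsy. The documents do not support that. The sentence in section 3.4 is stock text, nearly the same at every follow-up visit. At visit 4 it also lists photographs, which the section has already placed before the biopsy. It is a list of activities, not a sequence, and section 4.2 puts the rating before the visit.

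**Conclusion.** The point holds as a minor one. The rule for both scales has no restart after visit 4, so one comparison in four per scale (16 of 64) compares different wounds and can mislabel them. The count assumes that all 8 patients complete and that each wound has the five ratings in Table 1. The measures lie outside both primary objectives, and preference is asked separately.

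The missing reference period is a secondary matter that depends on an unseen form and on how patients read the question. Its size, under the since-last-visit reading only, is 4 of 16 rating pairs. If the form gives no reference period, none can be recovered for ratings already given.

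Three stronger readings are tempting and are not supported:

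- **That 7 of 16 pairs conflict with the patient's answer.** This is reached only by adding (1, 1), (2, 2) and (4, 4), which receive neither label under the rule. The absence of a label is not a contradictory label.
- **That the lack of an earlier rating at week 1, or the lack of room to improve from the best scores, is a further defect.** Both are ordinary properties of change scores on a bounded scale. For a severity score such as the pruritus NRS, change scoring within a cycle is legitimate.
- **That the overall-scale labels should be dropped altogether.** The established fault lies in the comparisons that cross the biopsy. Those within a cycle can stay.

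**What to change.** In section 4.2, Wound specific variables, add wording to this effect for both scales: no improvement or worsening label is computed across the visit 4 biopsy, and comparisons restart with the first rating of the new wound. State that the week 4 rating is taken before the biopsy, in line with the timing already given there. The first rating of the new wound is then week 6, and week 12 is compared with it.

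Make the main summary the raw rating for each wound at each visit, with the within-patient comparison of the collagen and sutured wounds. If the patient form gives no reference period, add a line saying that each overall rating refers to the most recent wounding: week 0 for weeks 1, 2 and 4, and the visit 4 biopsy for weeks 6 and 12. For ratings already collected without one, the report should say so.

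The cost is 16 labels per scale, leaving 48, plus about three sentences and possibly one line on the form. No new data or visits are needed.

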## **Study Population**

### **3.2 Sample Size, Inclusion and Exclusion criteria**

We will enroll a total of 8 patients for this study. The inclusion and exclusion criteria for the study are as follows:

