## 4.3 Statistical Considerations

Since this is a pilot study, we will perform only basic descriptive statistical analysis of our results. Due to the small number of subjects, it is unlikely that any statistical test would have the power to detect a significant difference in any of the measured variables. Instead, we will look at

wound closure, quality of forming scar histologically, and assess patient experience and preference. The results of this project may lead to the development of larger studies that will have the statistical power to detect significant differences in these variables after treatment with Nuvagen™ (collagen powder).

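### The patient overall scale has no answer for slight improvement, and the 1-point change rule can turn inconsistent rounding between visits into a change label

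*Combined protocol and SAP*

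**What the plan says.** The Patient Overall Assessment Scale is defined in Section 4.2 (Wound specific variables): "Patients will assess the overall improvement of their wounds using a 4-point scale". The levels are "1 = excellent improvement, 2 = good / moderate improvement, 3 = no change, 4 = worsening". On timing, the same paragraph says "This assessment will be performed prior to every follow up visit after wounding at week 0, and upon study completion for each wound". Table 1 places the ratings at weeks 1, 2, 4, 6 and 12, with none at week 0.

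The paragraph then adds a change rule. A fall of at least 1 point counts as improvement and a rise of at least 1 point as worsening, each judged against the preceding rating: "point compared to the previous assessment. Worsening will be indicated by an increase in this scale by" at least 1 point.

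Section 4.3 says "we will perform only basic descriptive statistical analysis of our results" and names what will be looked at: "wound closure, quality of forming scar histologically, and assess patient experience and preference". Section 4.2 calls the pruritus scale validated. It makes no such statement about this scale and cites no source for it.

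**The concern.** The answers are not exhaustive. On the ordinary meaning of the words, a slight improvement is neither good or moderate nor absent. The protocol does not tell the patient what to tick in that case, and different patients may settle it differently.

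The gap lies between two answers that are exactly 1 point apart, and 1 point is the amount the plan counts as a change. Rounding can therefore enter the results twice: in the recorded category, and in the improved or worse label derived from it.

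Patient experience is one of the few results Section 4.3 names. With a descriptive analysis, the recorded categories are themselves the result, and an answer that was never offered cannot be recovered later. Section 3.6 presents the pilot as a possible step towards larger studies, which could inherit the instrument.

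**Working it through.** The plan states no figure for this scale, so there is none to reproduce. The check applies the plan's own rule to a slightly improved wound.

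**Inputs from the documents**
- Levels 1 to 4 and the 1-point threshold: Section 4.2.
- Patients: "We will enroll a total of 8 patients for this study" (Section 3.2), each with two wounds.
- Ratings: 5 per wound (Table 1), which gives 4 consecutive pairs.
- Totals: 8 × 2 × 5 = 80 ratings and 8 × 2 × 4 = 64 pairs. The plan does not say whether the week 6 rating, after the week 4 re-biopsy, is compared with the week 4 rating. Without that pair the count is 8 × 2 × 3 = 48.

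**Step 1: what the rule does.** The wound is slightly better at the current visit, so the patient ticks 2 or 3. The difference is current minus previous.

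| Previous | Ticks 2 | Ticks 3 |
|---|---|---|
| 1 | +1, worsening | +2, worsening |
| 2 | 0, none | +1, worsening |
| 3 | -1, improvement | 0, none |
| 4 | -2, improvement | -1, improvement |

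Six of the eight combinations meet a threshold. In four of them (previous 1 or 4) the label is the same whichever answer is ticked. Only after a previous 2 or 3 does the forced choice decide the label, and then only if the answer changes.

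**Step 2: two successive slight ratings.** Assume the patient ticks 2 with probability p and 3 with probability 1 - p, independently at each visit. Then

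P(labelled improved) = P(3 then 2) = p(1-p)

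P(labelled worse) = P(2 then 3) = p(1-p)

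P(any label) = 2p(1-p)

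- p = 0.1 or 0.9: 2 × 0.1 × 0.9 = 0.18
- p = 0.25 or 0.75: 2 × 0.25 × 0.75 = 0.375
- p = 0.5: 2 × 0.5 × 0.5 = 0.50, the maximum
- p = 0 or 1 (always rounds the same way): 0

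**Step 3: scale over the trial.** The share s of ratings that are truly slight is not in the documents. Take s = 10% to 30% as an assumption.
- Ratings without a fitting answer: 80 × 0.10 = 8 to 80 × 0.30 = 24.
- If slight occurs independently across visits, the expected number of slight-slight pairs is 64 × 0.10² = 0.64 to 64 × 0.30² = 5.76. At a flag probability of 0.18 this gives about 0.1 to 1.0 flagged pairs; at 0.50, about 0.3 to 2.9.
- If instead the slight ratings all belong to wounds that are slight at every visit, there are 64 × 0.10 = 6.4 to 64 × 0.30 = 19.2 such pairs. The flagged pairs are then about 1.2 to 3.5 at 0.18, and 3.2 to 9.6 at 0.50.

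**Step 4: would a fifth level be enough?** With a slight-improvement level used consistently, two successive slight ratings differ by 0 and nothing is flagged. Adjacent answers would still be 1 point apart, so a patient wavering between slight improvement and no change would still meet the threshold. The rule also takes differences of a scale that already rates change. An answer of 1 followed by 2 is called worsening although the patient reports good or moderate improvement, and a wound rated 1 at every visit never counts as improved. A new level repairs neither.

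**The case against.** Any short ordinal scale forces rounding, and level 2 could be read as the answer for any improvement short of excellent. That makes the gap a matter of granularity, but it does not remove it: the wording of level 2 does not extend to slight improvement, and no instruction extends it.

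A reader might infer that the forced choice by itself always meets the 1-point threshold. It does not. The rule compares consecutive answers, so a patient who rounds consistently never receives a label from this cause. The same patient rating the same wound may well be consistent, which is also why independence between visits is a weak assumption.

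A reader might also take half as the expected rate of false labels. It is the maximum of 2p(1-p), reached only at p = 0.5.

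Whether a label is false depends on the reference point, which Section 4.2 does not give. If patients rate improvement since the last visit, a wound slightly better at two visits did improve, and an improved label is not wrong about the wound. A worsening label would still be wrong, and either label would still come from rounding.

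A third tempting inference is that the gap biases the comparison, because an open wound fills gradually while a sutured one starts closed. No section says that slight improvement is more frequent in the collagen wound. Sutured wounds also heal over time, and their sutures come out at visits 3 and 5. No direction can be claimed.

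Finally, the stakes are limited. Both objectives in Section 1 rest on clinical closure and histology. Healing is also measured from photographs, and patient experience is also captured by pruritus and preference. This stands and limits the weight of the point.

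**Conclusion.** The point holds as a minor measurement flaw. The missing answer is plain from Section 4.2, nothing elsewhere fills it, and the two answers on either side differ by exactly the amount the plan counts as change. Slight improvement is misrecorded whenever it occurs. A change label results from rounding alone only when a patient rounds differently at two visits, with probability between 0 and 0.50 for a slight-slight pair under the assumed independent model. The trial-level counts rest wholly on assumed values of p and s and on how far slight ratings persist, so they show scale and are not estimates.

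Most of the mislabelling comes from taking differences of a scale that already rates change, so the missing level and the differencing rule should be settled together. No decision rule depends on this scale, and the conclusions on closure and histology are unaffected.

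**What to change.** Make two edits to the Patient Overall Assessment Scale paragraph in Section 4.2, and match the patient form, before the first patient.

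1. Keep levels 1 and 2 as they are, insert slight improvement as a new level 3, and renumber no change to 4 and worsening to 5.
2. Delete the two sentences that define improvement and worsening by a difference of 1 point or more from the preceding rating. In their place, state that the chosen category will be reported for each wound at each visit, and that the two wounds of the same patient will be compared at the same visit.

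The second edit is needed as well as the first, because a five-level scale under the existing rule would still turn a one-step wobble into a change label.

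The cost is one more tick-box and a few lines of text. No visit or treatment step changes. The downside is that ratings would not be comparable with any earlier use of the 4-point version.

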## 4.2 Data Collection

All data variables will be stored in a secure database using coded identifiers in place of name. Most of the data will initially be recorded on approved study forms containing the participant's study ID code. After transfer of data into the computerized database, all paper forms will be kept in a secure locked cabinet within a locked office within the department. Photographs will be stored with a secure electronic file and will be labeled with the participant's study ID code and date they were taken.

## 4.3 Statistical Considerations

Since this is a pilot study, we will perform only basic descriptive statistical analysis of our results. Due to the small number of subjects, it is unlikely that any statistical test would have the power to detect a significant difference in any of the measured variables. Instead, we will look at

wound closure, quality of forming scar histologically, and assess patient experience and preference. The results of this project may lead to the development of larger studies that will have the statistical power to detect significant differences in these variables after treatment with Nuvagen™ (collagen powder).

